PVA is understudied in children, even though it may be more common and goes largely unrecognized even by highly trained clinicians. Moreover, existing pediatric studies have failed to identify a clear relationship between PVA and worse clinical outcomes, although these studies have not focused on the highest risk patients (such as those with Acute Respiratory Distress Syndrome (ARDS)), have used different definitions for PVA and its subtypes, and have been inadequately powered to evaluate the relationship between PVA subtypes and outcome. As part of this additional analyses under the REDvent study, we seek to fill crucial knowledge and implementation gaps including: (1) harmonizing how PVA is measured and defined, (2) identifying the most harmful PVA subtypes and the patients at risk, and (3) using innovative and accurate bedside tools to improve the recognition of PVA. We will leverage the expertise and preliminary data from three premier pediatric research groups who have the expertise to use precise methods to capture the patient's neural respiratory effort, which is crucial to correctly identify PVA subtypes. We will perform detailed secondary analysis of existing waveforms and clinical data from over 350 children, including all children enrolled in the REDvent study. We will use causal inference and mediation approaches to evaluate the relationship between PVA subtypes and clinical and mechanistic outcomes by leveraging data from the randomized controlled REDvent trial where PVA rates and subtypes likely differ between intervention and control groups.

Three existing datasets will be used as part of model and definition development, and data from the REDvent trial has more extensive clinical outcome and mechanistic data and will be used for additional analyses. Each dataset will contain one of three direct measures of patient neural respiratory effort (Pes, Children's Hospital Los Angeles; Edi, St. Justine Children's Hospital; sEMG, Beatrix Children's Hospital). The data which will be used for analysis has already been collected as part of the parent studies, or is planned for collection for the remaining patients in the REDvent trial.

Specific Aims

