patients and 54,284 breaths from the REDvent cohort at CHLA), 28.7% of breaths had some form of asynchrony, with 63/65 (95.4%) patients demonstrating at least one episode of PVA. The predominant asynchrony subtypes were flow undershoot (13.8%), delayed termination (7.4%), premature termination (5.1%), and reverse trigger (1.9%). Double cycled breaths occurred 3% of the time (see below). In a mixed cohort of 74 children at Beatrix Children's Hospital that used sEMG, 33% of breaths had some form of asynchrony. The predominant asynchrony subtypes were ineffective trigger (68%) followed by delayed termination (19%). DC breaths occurred 4% of the time. In a mixed cohort of 62 children at St. Justine Children's hospital that used Edi, 27% of breaths had some form of asynchrony. The predominant asynchrony subtypes were trigger delay (9%), ineffective efforts (10%) and premature termination (4%). DC breaths occurred 1% of the time. There are high rates of PVA amongst ventilated children, with differences in PVA subtypes based on institution, technique of measurement of neural effort, and disease state. These findings underscore the need to have common operational definitions for PVA subtypes which can incorporate different methods to measure neural effort, with a diverse, heterogeneous sample of ventilated children from multiple institutions.

Double Cycle (DC) occurs in approximately 3% of breaths, with underlying asynchrony subtypes nearly equally split between Reverse Trigger and Premature

Termination/Flow Undershoot. A DC breath occurs when the ventilator delivers a second breath before the patient has fully exhaled. This is particularly injurious because it leads to very high tidal volumes and risk of volutrauma (strain), in addition to high transpulmonary pressure and barotrauma (stress).^{21,22,24,48-51,60} In the REDvent cohort, 3.0% of breaths were DC, with at least one DC breath occurring in 46/65 (70.8%) patients. The most common PVA associated with DC breaths was reverse trigger (52.5%). High patient effort with flow undershoot/premature termination was also very common (45.2%, combined for analysis), while auto trigger (1.2%) was rare. Rates of DC breaths were similar in cohorts from St. Justine (1%) and Groningen (4%), but the underlying PVA subtype was not characterized.

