Analysis of PVA subtypes leading to DC breaths, and identification of risk factors: Each dataset contains detailed diagnostic data, demographics, ventilator settings, and medication data. Using data from existing datasets, all patients and all days of ventilation will be analyzed to describe the frequency of PVA subtypes leading to DC breaths. For each DC breath (anticipated 3% of all breaths), one of three underlying PVA subtypes will be annotated (Reverse Trigger, Flow Undershoot/Premature Termination, Auto-trigger, Figure 4). Flow undershoot and premature termination represent the same physiologic concepts of inadequate ventilator support, so they will be combined for analysis of DC breaths. We anticipate that RT and Flow Undershoot/Premature Termination will continue to comprise $> 95\%$ of the causes of DC and will be the primary focus of analysis. We will evaluate ventilator and patient specific risk factors for PVA subtypes which lead to DC.

Sample Size and Power: From existing datasets, we are anticipating having over 1,000,000 breaths for analysis, from 371 patients, with more than 1,000 patient days. Based on our preliminary data, 3% of breaths are DC, and 70% of patients have at least one episode of DC. This should give us a minimum of 30,000 DC breaths from 260 patients. This will permit inclusion of dozens of variables in the risk factor analyses, although we anticipate between 3-5 in each model. Analysis will be conducted on the breath and on the patient level.

The goal of the breath level model is to understand why DC occurs when a specific PVA subtype is present. We will create two prediction models, one to identify risk factors for DC related to RT and one to identify DC related to flow undershoot/premature termination. Variables considered in the breath-by-breath model include parameters with biological plausibility to be in the causal pathway for the PVA subtype or DC including ventilator mode (including NAVA), respiratory rate, ventilator rate (RRvent), spontaneous or neural respiratory rate (RRneural) and neural

Asynchrony subtypes leading to Double Cycled Breaths

[figure not shown]

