Figure 4. Asynchrony subtypes leading to DC breaths. Flow undershoot/ premature termination represent inadequate ventilator support for the patient's respiratory drive, while Reverse trigger leading to DC occurs when patient effort begins after lung insufflation. Auto trigger is relatively rare and occurs when a second breath is delivered with no patient effort.

initiation and termination, peak inspiratory pressure (PIP), Tidal Volume, PEEP, inspiratory time, and an estimate for patient effort (Δ Pes, peak Edi, or sEMG). We will first perform univariate analysis on the predictor variables of interest, stratified by DC versus non-DC in each of the subtypes. Mixed logistic regression models will then be created to first control for patient level effects with repeated measurements per patient, retaining variables with an independent association with DC breaths.

The goal of the patient level model is to identify patients who are at high risk for DC. Because RT and flow undershoot/ premature termination are the PVA subtypes which lead to DC over 95% of the time, variables for consideration will focus on risk factors for each of these PVA subtypes, in addition to risk factors for DC specifically. Univariable analysis will examine the Spearman's correlation between the frequency of DC breaths per patient in each PVA subtype category and static patient related variables of interest such as **age**, **gender**, height, body weight, risk factors and severity of lung injury, blood gas data, sedation and analgesia (cumulative dose of drugs, pain and sedation scale). In addition, median values for respiratory parameters from breath-by-breath analysis over the entire 30-minute recording will also be used. Subsequently, patients will be categorized into groups based on the frequency of DC breaths from each subtype. Those with DC occurring in more than 5% of breaths will be labeled DC patients for analysis. Our preliminary data supports this occurs in approximately 20% of patients. Subsequently, mixed logistic regression models will be created to identify the patient specific factors associated with DC, stratified by each of the PVA subtypes.

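### Asynchrony Aim 1 pools three hospitals, each with its own effort sensor, and names no hospital term and no common effort scale, so hospital differences can pass for risk factors for double cycling

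*Combined protocol and SAP*

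**What the plan says.** All references are to section H of the current protocol, the secondary asynchrony analyses.

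- **Three datasets, one sensor each.** The summary and rationale states: "Each dataset will contain one of three direct measures of patient neural respiratory effort". Pes belongs to the Los Angeles hospital (REDvent), Edi and sEMG to one other hospital each. Hospital and sensor are therefore the same variable.
- **One pool.** The Aim 1 sample-size paragraph reads: "From existing datasets, we are anticipating having over 1,000,000 breaths for analysis, from 371 patients, with more than 1,000 patient days".
- **Known heterogeneity.** The Aim 1 preliminary data report high asynchrony rates "with differences in PVA subtypes based on institution, technique of measurement of neural effort, and disease state". Double-cycled (DC) breaths are given as 3.0% at the Pes hospital, 4% at the sEMG hospital and 1% at the Edi hospital. The text calls the rates at the last two similar to REDvent's, and notes that the subtype behind their DC breaths was not characterised. Both are described as mixed cohorts.
- **Breath-level model.** Mixed logistic regression controls for repeated measures within patient. One listed candidate predictor is "an estimate for patient effort (Δ Pes, peak Edi, or sEMG"; no rescaling or sensor-specific term is stated.
- **Patient-level analysis.** Spearman correlations come first. Children with DC in more than 5% of breaths (about 20%) are then labelled DC patients, and "mixed logistic regression models will be created to identify the patient specific factors associated with DC, stratified by each of the PVA subtypes". The random effect is not named, and the stratification is by asynchrony subtype, not by hospital.
- **Harmonisation.** Definitions are extended to all three sensors, and reader agreement is checked per subtype and sensor before annotation proceeds.

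**The concern.** When units from several sources are pooled and both the outcome rate and the case mix differ by source, any predictor whose mean also differs by source picks up the difference. Age, severity of lung injury, sedation practice, ventilator mode and set rate could all plausibly differ between a trial cohort selected for hypoxaemic lung disease and two mixed cohorts.

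A patient random intercept deals with repeated breaths. It does not remove this confounding, because it is assumed independent of the predictors. Harmonised labels make the outcome comparable, but they adjust no predictor and do not rescale effort.

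The effort variable has a second problem. Delta Pes is a pressure, while Edi and sEMG are electrical signals. Entered as one number, its coefficient mixes three units and partly codes the hospital.

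Aim 1 exists to find ventilator and patient factors behind DC. A factor that only marks a hospital or sensor would be a poor lead for later work.

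**Working it through.** **Reproducing the plan's figures.** The inputs are "3% of breaths are DC, and 70% of patients have at least one episode of DC".

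- DC breaths: 0.03 × 1,000,000 = 30,000. Patients: 0.70 × 371 = 259.7, or 260. Both match: "This should give us a minimum of 30,000 DC breaths from 260 patients".
- Cohort sizes: 235 + 74 + 62 = 371. The 74 (sEMG) and 62 (Edi) are in the Aim 1 preliminary data. The 235 is stated under Aim 2; its use here is inferred from the exact sum.
- The yield applies REDvent's 3% to all three hospitals. Weighting by hospital, with equal breaths per child assumed: (235 × 3% + 74 × 4% + 62 × 1%) / 371 = 2.87%, or about 28,650 DC breaths.
- Odds ratio for a DC breath against the Edi hospital: (0.03/0.97)/(0.01/0.99) = 3.1 for Pes and (0.04/0.96)/(0.01/0.99) = 4.1 for sEMG.

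**False positives for a predictor with no effect within any hospital.** Two simulations used sizes 235/74/62, DC means 3%/4%/1%, outcome DC in more than 5% of breaths, and two-sided 0.05. The per-child DC distribution and the predictor shifts are assumptions.

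- Simulation A: exponential DC share, so P(>5%) at the Pes hospital is exp(−5/3) = 19%; 1,500 runs per scenario.
- Simulation B: beta DC share with precision 20, giving 20.1% above 5% at the Pes hospital; 2,700 breaths per child (1,000,000/371 ≈ 2,695); 2,000 runs.

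| Shift in predictor mean (sEMG / Edi hospital, SD) | Simulation | Pooled logistic | Pooled Spearman |
|---|---|---|---|
| 0 / 0 | B | 5.5% | 5% |
| 0 / 0.25 | B | 6% | 10% |
| 0 / 0.5 | B | 8% | 25% |
| +0.3 / −0.3 | A | 12% | 18% |
| +0.5 / −0.5 | A; B | 24%; 17% | 42%; 50% |
| 0 / 1 | A; B | 26%; 17% | 59%; 66% |
| +1 / −1 | B | 42% | 94% |

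With no shift, A gave 5–6%. When both smaller hospitals shift the same way, A gave 5–13%. With hospital strata (A) or hospital indicators in the logistic model (B), the rate was 4–6% throughout.

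**Effort variable.** True odds ratio 1.5 per within-hospital SD, 1,000 runs, purely illustrative scales given as mean (SD). Pooled odds ratios are per pooled SD.

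| Pes | sEMG | Edi | Pooled OR | Result |
|---|---|---|---|---|
| 10 (5) | 10 (5) | 10 (5) | 1.48 | power 82% |
| 10 (5) | 5 (3) | 15 (10) | 1.08 | power 7% |
| 10 (5) | 5 (3) | 30 (10) | 0.82 | significant in the wrong direction in 22% of runs |
| 10 (5) | 20 (10) | 5 (3) | 1.67 | inflated |

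Standardised within hospital and with hospital terms, power was 83–86% in all four.

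**Events available.** 20% of 371 = 74 DC patients. Splitting them by REDvent's breath shares (52.5% reverse trigger, 45.2% flow undershoot/premature termination; applying these to patients is an assumption) gives about 39 and 34. With five predictors: 39/5 = 7.8 and 33.5/5 = 6.7 events per variable. With two hospital indicators added: 39/7 = 5.6 and 33.5/7 = 4.8.

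**The case against.** - **The protocol does not say DC rates differ by institution.** A reader might infer that it does. The sentence on differences concerns asynchrony subtypes, and DC rates are called similar. This stands. The 3% against 4% contrast may be chance, and the 1% hospital drives most of the effect.
- **The rates predate harmonisation.** How much of the gap would survive common definitions is unknown. This stands, and it limits the simulations.
- **A hospital effect is not excluded.** The patient-level random effect is unnamed, and the variable lists are open and include lung-injury severity. That makes this a gap in specification, not a proven omission. Even so, the plan itself points to institution and technique, and a random effect with three levels would be poorly estimated.
- **The breath-level model is less exposed.** It asks why DC occurs given a subtype. For predictors that vary breath to breath, many breaths per child mean that it relies mainly on within-child contrasts. This stands; the exposure there is confined to predictors that vary little within a child. The simulations cover only single-predictor patient-level analyses of total DC, not the planned subtype-stratified models with 3–5 variables.
- **Spearman is only the univariable step.** Its larger error rates do not by themselves produce an independent risk factor. This is correct.
- **Effort may be meant sensor by sensor.** No passage says that raw values share one scale. None says otherwise either.
- **Hospital terms may separate.** Under simulation A the Edi hospital expects 62 × exp(−5) = 0.4 DC children, with a chance of none of (1 − exp(−5))^62 ≈ 66%. Under simulation B, with 5.3% above the cut-off, that chance is about 3%. The problem is real but manageable: a hospital without events simply adds no information on the other coefficients.

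**Conclusion.** The point holds as a specification gap in a secondary analysis. As written, Aim 1 can confound risk factors for DC with hospital or sensor, mainly in the patient-level models, in the pooled Spearman correlations, and for breath-level predictors that vary little within a child. The pooled effort coefficient has no common unit.

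The size is conditional. It ranges from near the nominal 5% (small or same-direction shifts) to 17–26% for logistic models and 42–66% for Spearman under the ±0.5 SD opposite-direction and 1 SD single-hospital scenarios. This rests on the unharmonised DC rates, on assumed per-child distributions, and on assumed predictor shifts that cannot be derived from the documents.

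A reader might go further and conclude that hospital differences will be reported as risk factors. The documents do not support that, because bias requires a predictor to differ between hospitals by an amount that they do not state. Nor does the point reach the randomised comparison or the primary outcome.

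**What to change.** Amend the Aim 1 analysis text in section H:

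1. Include hospital/sensor (three levels) as a fixed term or stratum in the breath-level and patient-level models. Where a hospital has few or no DC children, use conditional or Firth logistic regression; the SAP already provides for Firth's method when event rates are small in subgroups.
2. Compute Spearman correlations within hospital and combine them.
3. Standardise effort within sensor, or fit a sensor-specific slope.
4. Report factors that vary only between hospitals as not separable from hospital.
5. Name the random effect in the patient-level model.

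No new data are needed. The cost is fewer events per variable in the subtype-stratified patient models (about 5–6 instead of 7–8) and wider intervals for factors that vary mainly between hospitals. Genuine between-hospital contrasts, such as in mode or set rate, would no longer contribute, which argues for keeping each patient model small.

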Consenting subjects will be **block randomized** to intervention or control arms for the acute phase based on age group: infant (30 days -365 days), child (366 days to \leq 8 years), and older child/ adolescent (9-21 years); and immune suppression. For study purposes immune suppressed patients will be defined as: patients with congenital or acquired conditions (including medications) which result in marked inability to respond to antigenic stimuli. Examples of immune suppression include: oncologic disease with recent chemotherapy or radiation, congenital immunodeficiency, HIV, rheumatologic condition on chemotherapy, allogeneic or autologous stem cell transplant, solid organ transplant, or any other condition in which immunosuppressive medications are prescribed. Block randomization will be based on random block sizes of 4, 6 and 8 within the strata above, and loaded into opaque envelopes by the statistician for the study team to determine treatment arm at the time of randomization. Weaning phase randomization will be block randomized by REDvent-acute phase group, age, and immunosuppressed status using the same methodology. Although **blinding** is not possible given the open label nature of the intervention, analysis will be blinded to treatment groups, and performed by an independent statistician.

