Figure 7: (a, top left) Length of ventilation (days) is higher in children with flow undershoot forms of PVA when spontaneous breathing does not occur until after the 3rd day of ventilation (b, top right) Diaphragm hypertrophy may be more likely to occur in children with flow-undershoot forms of PVA (c, bottom left) Delirium scores are higher in children with high rates of Double Cycled breaths. (d, bottom right) Reverse Trigger patients receive higher doses of opioids.

Methods and Analysis Hypothesis A: Here we seek to test whether the REDvent intervention results in different rates and subtypes of PVA than usual care. This type of analysis is perfectly suited to secondary analysis of a randomized trial, where the intervention is striving to promote more spontaneous breathing with a downstream influence on PVA. This would not be possible to do with an observational cohort, because of inherent selection bias in which patients are permitted to have more spontaneous breathing. We believe the forms of asynchrony which lead to DC breaths (flow undershoot/premature cycling) and reverse trigger may be different in REDvent versus control patients. This aim will use all available patients with spontaneous breathing in the REDvent dataset (expected 235). For each patient day with spontaneous breathing, PVA subtypes will be analyzed. The proportion of breaths which fall into a particular PVA subtype will be expressed in addition to global asynchrony index, calculated as the total number of asynchronous breaths over the total number of breaths.³⁰ Because rates of PVA may vary from day to day, analysis will focus on both an area under the curve of PVA over all days (calculated as the total number of asynchronous breaths over the total number of breaths available for analysis) in addition

to the highest rate of PVA on any day for each patient, by PVA subtype. PVA and PVA subtype rates per patient will be expressed as a continuous variable and compared between REDvent and usual care patients using a Mann Whitney U test given it is not expected to be normally distributed. PVA subtypes which are different between REDvent and control patients will be considered for mediation analysis (below).

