The analytic approach for secondary aims and outcomes such as mortality and ventilator free days will follow those described above. For categorical data, a χ^2 or Fisher's exact test will be used to compare difference between groups. Logistic regression will be used to assess binary outcomes, and a multinomial/ordinal logistic regression will be used for categorical outcomes (> 2 categories) while adjusting for covariates. To assess the association between 2 continuous variables, a Pearson or Spearman correlation will be used, and analysis of covariance (ANCOVA) will be used to adjust for covariates. Generalized Estimating Equations (GEE) or mixed effect models will be used when necessary to analyze repeated measures. Because of the physiologic nature of the study with a Phase II design,

multiple comparisons adjustment is not planned for secondary outcomes. Analyses will be performed using the appropriate recent version of the SAS statistical software (SAS Institute Inc., Cary, NC).

In order to increase precision around the effect estimates for the primary and secondary aims and to reflect the stratified sampling, all analyses are adjusted for block randomization variables.³ For acute phase these are age group (infant, child, and adolescent) and whether or not the subject was immunocompromised. For the weaning phase this is acute phase randomization grouping and age group. In addition, variables thought to be potential confounders on the relationship between intervention and outcome with large differences between groups (standardized effect sizes as detailed above) will also be included in all adjusted analyses. Unadjusted analyses will be presented to summarize data; all primary and secondary outcomes will present adjusted analyses controlling for age category, immunosuppression and imbalanced baseline variables. Potential confounders will be assessed for multicollinearity and if present, the confounder with the highest biological plausibility to impact the effect of the intervention on the outcome will be selected for inclusion as a model covariate.

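### Asynchrony Aim 2, Hypothesis A compares arms with a Mann-Whitney test that leaves out the randomisation strata; a stratified or adjusted rank analysis is an almost free improvement, worth 0 to about 8 points of power

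*Combined protocol and SAP*

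**What the plan says.** Protocol Section H, Methods and Analysis Hypothesis A, takes all REDvent patients with spontaneous breathing (235 expected). Each patient gets a rate over all days, and the analysis extends "to the highest rate of PVA on any day for each patient, by PVA subtype". These rates are then "compared between REDvent and usual care patients using a Mann Whitney U test given it is not expected to be normally distributed". No strata, covariates or significance threshold are named. On the use of the result: "PVA subtypes which are different between REDvent and control patients will be considered for mediation analysis (below". The next paragraph models the REDvent effect on length of ventilation (competing risks), PiMax (linear) and mortality (logistic), then adds the selected subtypes. A subtype counts as a mediator if it moves the REDvent estimate by more than 20%. No blocking variables are named there either.

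Allocation was stratified. The July 2024 SAP (Randomization Strategy and Blinding) gives 1:1 blocks of 4, 6 and 8 within three age groups and immune status for the acute phase. Protocol D.6.1 adds: "Weaning phase randomization will be block randomized by REDvent-acute phase group, age, and immunosuppressed status using the same methodology".

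The SAP's adjustment rule is that "all analyses are adjusted for block randomization variables". It ties the rule to precision for the primary and secondary aims and to the stratified design. It also says "Unadjusted analyses will be presented to summarize data", and requires adjusted results for every primary and secondary outcome. SAP Table 1 carries this out: its models for IMV duration, PiMax, ICU mortality and 90-day mortality all control for the blocking variables.

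**The concern.** When allocation is balanced within strata and the strata predict the outcome, the between-arm difference varies less than an unstratified test assumes. The plain test then rejects too rarely under the null and has less power than an analysis that uses the strata. Here the test also acts as a filter, because its result determines which subtypes are considered for mediation. A real difference missed at this step may not be examined as a mediator.

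The same omission runs into the models that follow. The 20% rule is applied to a REDvent estimate. If that estimate comes from a model without the blocking variables, it will not be the estimate the trial reports for closely matching outcomes.

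**Working it through.** **No figure in the plan to reproduce.** Section H gives no power for the Mann-Whitney step. Its only power figure, 0.84, belongs to the mediation model and is not at issue here.

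**Inputs from the documents.** 276 enrolled and 235 analysed; six acute-phase strata (3 age groups × 2 immune states); 1:1 blocks of 4, 6 and 8. In the preliminary data 46 of 65 patients had any double-cycled breath, so 19/65 = 29% had none, and a 30%-zeros case was run.

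**Assumptions.** Two-sided alpha of 0.05, borrowed from the SAP's primary power statement. Equal age thirds and 35% immunosuppressed. The share of PVA variance explained by the strata (R²) is not in the documents, so it was varied from 0 to 0.30. The arm shift was set for about 0.80 power of the plain test at R² = 0: 2.8016 × √(4/235) / √(3/π) = 2.8016 × 0.1305 / 0.9772 = 0.374 SD.

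**Approximation under perfect stratum balance.** The standard deviation of the plain statistic shrinks to √(1 − R²).
- Type I error of the plain test = 2Φ(−1.96/√(1 − R²)).
- Power of the plain test = Φ((2.8016 − 1.96)/√(1 − R²)).
- Power of the adjusted test = Φ(2.8016/√(1 − R²) − 1.96).

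At R² = 0.20, √0.80 = 0.894. Type I error is 2Φ(−2.191) = 0.028, plain power 0.827 and adjusted power 0.879, a gap of 5.2 points.

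**Simulation.** 276 patients, stratified blocks, random retention to about 235; 6,000 runs for type I error and 4,000 for power. The plain Mann-Whitney test was compared with van Elteren and with rank regression on arm plus strata.

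| R² | Type I error: plain | Van Elteren / adjusted | Power: plain | Van Elteren / adjusted |
|---|---|---|---|---|
| 0 | 0.048 | 0.047 / 0.049 | 0.795 | 0.782 / 0.794 |
| 0.05 | 0.048 | 0.053 / 0.054 | 0.806 | 0.811 / 0.822 |
| 0.10 | 0.043 | 0.049 / 0.052 | 0.799 | 0.820 / 0.828 |
| 0.20 | 0.031 | 0.049 / 0.048 | 0.819 | 0.865 / 0.875 |
| 0.30 | 0.027 | 0.049 / 0.051 | 0.826 | 0.909 / 0.909 |

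The approximation and the simulation agree in direction and roughly in size. Simulation error is about 0.003 on type I error (√(0.05 × 0.95/6000)) and 0.006 on power (√(0.8 × 0.2/4000)). With 30% zeros the pattern is the same: at R² = 0.30, plain power is 0.808 against 0.891 / 0.896.

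**If stratum balance is lost.** Retention was set to 0.60-0.75 in the high-PVA strata of one arm and 0.90 elsewhere (illustrative). Type I error of the plain test was then 0.050-0.058 for R² from 0.10 to 0.30, so it was no longer conservative. The stratified and adjusted tests gave 0.044-0.055.

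**The case against.** The strongest reply is that an unstratified rank test after stratified randomisation is a common and usable choice, so any gain from stratifying is optional. Several stronger readings are tempting, and the documents do not support them.

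- **That the test is conservative and loses power as a matter of fact.** This needs strata that predict PVA. Section H lists age only as one of many candidate variables for double cycling and does not list immunosuppression. Protocol D.6.2 justifies the strata by weaning and ventilation duration. No stratum-PVA association is given, and R² may be near zero.
- **That Section H breaks the SAP.** The SAP sentence is framed for the primary and secondary aims, and PVA rates appear in neither SAP table. The SAP text itself also names a Mann-Whitney test for weaning duration. For PVA the conflict is arguable. It is stronger for the REDvent-effect models, because length of ventilation, PiMax and mortality have close SAP counterparts that all adjust. Even there, Section H leaves covariates unlisted rather than excluding them.
- **That a missed subtype is lost.** Section H says only that differing subtypes will be considered, and Hypothesis B still relates the subtypes to outcomes.
- **That the selection step as a whole is too strict.** Several subtypes and two summaries are tested with no threshold and no multiplicity control. At 0.05 each, four independent tests give a family-wise error of 1 − 0.95⁴ = 0.19 and eight give 0.34. These are upper-end figures, because the tests are correlated.

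These replies limit the size and certainty of the loss. They do not give a reason to leave the strata out: adjustment costs almost nothing at R² = 0, and imbalance in the spontaneous-breathing subset would itself be a reason to adjust.

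**Conclusion.** This is a free improvement, not an invalid analysis. The between-arm PVA test leaves out strata that were built into the randomisation, and it helps decide which subtypes reach mediation. The power at stake is nil at R² = 0, about 0-2 points at 0.05, 2-3 at 0.10, 5-6 at 0.20 and 8 at 0.30. The cost of stratifying at R² = 0 is about 1 point with van Elteren and 0.1 with covariate adjustment.

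The loss figures assume that the strata stay balanced among analysed patients. That is not guaranteed, since the intervention promotes spontaneous breathing and the set is conditioned on it. They cover the six acute-phase strata only, and rank regression stood in for the proportional-odds model, which was not itself simulated.

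**What to change.** 1. Reconcile the weaning-phase strata. Protocol D.6.1 lists acute-phase group, age and immunosuppression; the SAP's randomisation and adjustment paragraphs list only acute-phase group and age. Until this is settled, the adjustment set for a weaning-phase comparison is undefined.
2. State in Hypothesis A which randomisation defines REDvent versus usual care. Replace the Mann-Whitney test with a van Elteren test, or with the proportional-odds model the SAP already uses for PiMax, including the blocking variables of that randomisation.
3. Name the same blocking variables in the REDvent-effect and mediation models of Section H, in line with SAP Table 1 for IMV duration, PiMax and mortality.
4. State the threshold for calling a subtype different.

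The cost is a wording change in Section H and one reconciliation. The strata are known at randomisation and the proportional-odds model is already in the SAP, so no new data are needed.
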